8.1. Statistical analysis

Summary statistics will be generated to describe the study sample at baseline. Descriptive statistics, including measures of central tendency (e.g. means, medians) and estimates of spread (e.g., standard deviations, quartiles) will be used for continuous variables such as age and baseline HBV DNA and HBsAg levels. Frequency distributions will be used for categorical variables such as HBV genotype and HBeAg status. Ninety-five percent confidence intervals will be calculated for all point estimates of continuous data. Graphical displays (e.g. histograms, box plots) will also be used to describe the data. The baseline demographic information and viral characteristics will be compared between the two treatment arms using the chi-square test for association or exact tests for differences in proportions for categorical variables or using a test of trend

in ordinal data. Continuous variables may be transformed, where appropriate, to meet the assumptions of parametric tests. The Student's t-test or a non-parametric alternative, the Wilcoxon rank-sum test, will be used to determine differences in the distribution of continuous data between the two treatment arms.

Primary analyses will be performed using all enrolled participants (intention-to-treat analysis). Participants will be considered enrolled in the study upon being randomized to one of the two treatment arms.

For all analyses, a p-value of less than 0.05 will be used to indicate statistical significance.

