8.1.1. Analysis of primary endpoint

The primary endpoint is loss of HBsAg at week 240. The cumulative proportion of HBsAg loss at the designated time-point will be estimated using the product-limit (Kaplan-Meier) estimate. HBsAg loss between two treatment groups will be compared using a Wald-type two-sided two-sample proportion test (chi-square test).

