8.2. Missing data

Primary analyses will be performed using all enrolled participants (intention-to-treat analysis). For the primary analysis, the proportion of patients with HBsAg loss at the end of follow-up (week 240) will be estimated using the product limit (Kaplan-Meier) method which includes drop outs for as long as they are followed. Since our sample size estimation accounts for participants lost to follow up for various reasons, and due to randomization, the rate of missing is expected to be similar in the two treatment groups, we will also conduct the analysis of primary endpoint on the available cases. For this analysis, we will describe the treatment effects in terms of relative risks and 95% confidence intervals. In order to take into account the stratification at the randomization, we will use Mantel-Haenszel chi-square test. Comparison of rates of HBsAg loss across two treatment groups adjusting for other baseline demographic, virological and clinical characteristics such as age, race, genotype, HBeAg status, initial HBV DNA level, and baseline histology will be performed using multivariable log-linear (Poisson) regression, with HBsAg loss (Yes/No) as the outcome. The results will be presented as relative risks of HBsAg loss and their 95% confidence intervals.

In general, the procedure of missing outcome data will be handled as follows in statistical analyses. First, we will explore the pattern of missing data by comparing characteristics of participants with available data to those with missing data. For data missing completely at random (does not depend on observed outcome; MCAR) standard analytical techniques described earlier would produce unbiased results when the analysis is performed on the complete data. For the time-to-event data analyses, the analytical methods such as Kaplan-Meier method, log-rank test, and Cox proportional hazard model automatically accounts for MCAR drop-outs. However, in other cases, we will assume that the dropout depends on observed outcome and/or covariates (missing at random, MAR). For such scenarios, likelihood-based methods such as mixed models, generalized linear mixed models and logistic regression will provide unbiased inference. For GEE, we will draw inference using inverse-probability-weighting approach, with models fitted using the reciprocal of the estimated probability of missing as weights. The probability of missing will be estimated using logistic regression.

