8.3. Sample size and power

The sample size for this study was determined based on the primary endpoint of HBsAg-loss at 48 weeks after treatment has been stopped. There are no data available on HBsAg loss for long-term treatment with tenofovir DF or tenofovir DF and peginterferon combination therapy. We anticipate that after 192 weeks of treatment and 48 weeks of follow-up post-treatment 5% of the participants in the tenofovir DF alone group will achieve HBsAg loss compared to 15% participants in the tenofovir DF and peginterferon combination therapy group. The clinical trial would require 141 participants per arm (282 participants in total) to detect this expected difference with 80% power at 5% level of significance using a two-sided test of equality between two proportions (chi-square test). However, for this long-term treatment trial, it is expected that approximately 25% of the participants will be lost to follow-up and hence the study will recruit a total of 376 participants (randomized 1:1 to two treatment arms, 188 per arm) to account for the missing participants.

9. Data and safety monitoring board

Data and safety will be monitored by the NIDDK in conjunction with an NIDDK-appointed Data and Safety Monitoring Board (DSMB). This board serves in a consultative capacity to inform the NIDDK decisions regarding conduct of the study. The description of DSMB activities is included in the DSMB Charter.

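### The primary test pairs a Kaplan-Meier estimate with a test labelled chi-square, and states neither the variance nor any use of the randomisation strata

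*Combined protocol and SAP*

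**What the plan says.** Section 8.1.1 sets the endpoint ("The primary endpoint is loss of HBsAg at week 240") and the estimator: "The cumulative proportion of HBsAg loss at the designated time-point will be estimated using the product-limit (Kaplan-Meier) estimate". The test follows: "HBsAg loss between two treatment groups will be compared using a Wald-type two-sided two-sample proportion test (chi-square test". Section 8.2 confirms that the primary analysis covers all randomised participants and uses the "product limit (Kaplan-Meier) method which includes drop outs for as long as they are followed".

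Section 8.3 (Sample size and power) sizes the trial on 5% versus 15% HBsAg loss, at "80% power at 5% level of significance using a two-sided test of equality between two proportions (chi-square test"). It adds that "it is expected that approximately 25% of the participants will be lost to follow-up". Section 8.1 sets the level: "For all analyses, a p-value of less than 0.05 will be used to indicate statistical significance".

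Section 3 stratifies randomisation by HBeAg status, genotype (A or other) and cirrhosis. Strata are used in 8.1.2 (stratified log-rank and Cox), in 8.1.2.1 (Mantel-Haenszel) and in the available-case analysis of 8.2. Section 8.1.1 does not mention them. No section names a variance formula for the primary test, neither Greenwood nor binomial.

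**The concern.** An ordinary two-sample proportion test takes an event count and a denominator from each arm. A Kaplan-Meier proportion with censored participants has no such pair. It is less precise than a binomial proportion based on everyone randomised, because participants who leave early contribute only part of the follow-up. If the Kaplan-Meier proportions are put into the usual formula with 188 per arm, censored participants are treated as fully observed. The standard error is then too small and the test rejects too often.

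This is the trial's single confirmatory test, and its p-value cannot be reproduced from the text as it stands. The primary test is also the only HBsAg comparison in section 8 for which the plan does not say how the stratified randomisation enters.

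**Working it through.** **The plan's own figure.** Inputs from section 8.3: 5% versus 15%, two-sided 5%, 80% power. With pooled variance and no continuity correction:

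n = [1.960·√(2·0.10·0.90) + 0.842·√(0.05·0.95 + 0.15·0.85)]² / 0.10² = (0.832 + 0.352)² / 0.01 ≈ 140.1, rounded up to 141 per arm, or 282 in total.

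Allowing for 25% loss: 282 / 0.75 = 376, or 188 per arm. Both stated figures reproduce.

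**Size of the error under binomial variance.** Let K(t) be the probability of still being followed at time t, and T the time of HBsAg loss. For rare events Greenwood's variance is about Σ dᵢ/nᵢ². Its expectation is (F/n)·E[1/K(T)], where F is the week-240 proportion. The binomial variance is about F/n. The true variance therefore exceeds the binomial one by the ratio R = E[1/K(T)], and a nominal 5% test has actual level 2[1 − Φ(1.96/√R)].

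- Uniform events and uniform losses reaching 25%: R = −ln(0.75)/0.25 = 1.15. Level = 2[1 − Φ(1.827)] = 6.8%.
- All losses before any event: R = 1/0.75 = 1.33. Level = 2[1 − Φ(1.697)] = 9.0%. This is the approximate ceiling for 25% loss.
- All events before any loss: R = 1. Level = 5%.

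**Simulation check.** 20,000 trials per scenario, 188 per arm, 25% loss in each arm, equal true rates. Event and loss timing are assumptions. Entries are type I error for null rates of 5% / 10% / 15%.

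| Events | Losses | Binomial variance, n = 188 | Greenwood |
|---|---|---|---|
| uniform | uniform | 6.9 / 7.5 / 7.1% | 4.9 / 5.5 / 5.1% |
| uniform | early | 8.4 / 8.9 / 8.5% | 4.6 / 5.1 / 4.9% |
| late | early | 9.3 / 8.8 / 9.0% | 5.1 / 5.0 / 4.8% |
| late | around week 192 | 9.2 / 9.1 / 9.3% | 4.9 / 5.1 / 5.1% |
| early | around week 192 | 4.8 / 5.5 / 5.0% | 4.8 / 5.5 / 5.0% |

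Over all 27 combinations run, Greenwood gave 4.6% to 5.5%. An ordinary chi-square test gave 4.5% to 5.3% on observed events over 188, and 4.6% to 5.3% on available cases. With no loss, every version gave about 5%.

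**Power with Greenwood variance.** For 5% versus 15%, 188 per arm and 25% loss, power was 87% (uniform events and losses), 83% (late events, uniform losses) and 82% (late events, early losses).

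**Sparse strata.** Three two-level factors give 2·2·2 = 8 strata. At 5%, a control arm of 188 yields about 9.4 events. With equal strata (an assumption) each holds 188/8 = 23.5 control participants, and the chance of no event in a given one is 0.95^23.5 ≈ 0.30. The chance that at least one of the eight has none is 1 − 0.70⁸ ≈ 0.94. Greenwood variance in such a stratum is zero. In one simulated sparse-strata scenario, combining Greenwood-based differences over all eight strata gave about 7% under the null.

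**The case against.** The strongest defence is that the plan already allows the right test. A Wald statistic is an estimate divided by its own standard error, and its square is referred to chi-square on 1 degree of freedom. Directly after a Kaplan-Meier sentence, the natural standard error is Greenwood's. The count-based tests in 8.1.2.1 and in the sample-size section say chi-square without Wald-type, so the different wording may be deliberate. All of this stands, and it means the plan cannot be said to prescribe binomial variance.

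It does not settle the matter. A Wald test of two proportions is also the textbook name for a difference over its unpooled binomial standard error. Section 8.1.2.1 uses nearly the same label for ordinary binary endpoints, and the sample-size section sizes this very endpoint with an ordinary chi-square test. Two variances remain open.

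A reader might also infer that the analyst could choose afterwards among Kaplan-Meier, events over 188 with drop-outs taken as no loss, and completers only. Section 8.2 does not support that. Drop-outs enter "which includes drop outs for as long as they are followed", which excludes counting them as failures, and the available-case analysis is an additional one with its own Mantel-Haenszel test. Both count-based tests also held about 5% with equal loss in the arms.

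**Conclusion.** The primary test is under-specified in two respects: its variance, and its handling of the randomisation strata. A reader might conclude that the plan inflates type I error. The documents do not support that: inflation arises only if binomial variance on all 188 per arm is applied to the Kaplan-Meier proportions. Under that reading the level is about 7% with uniform events and losses, up to about 9% when losses precede events, and about 5% when events come early and losses late. Simulated values slightly over 9% are consistent with the approximate ceiling of 9.0% and do not point to a larger effect.

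These figures rest on 25% loss in each arm (section 8.3, with similar loss by arm expected in 8.2) and on assumed timing. The plan gives no distribution of event or loss times. Its only pointer is in section 9.1, which expects the endpoint to be very rare during treatment; that favours late events and the upper part of the range. The sample size of 141 evaluable and 188 recruited per arm is not affected.

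**What to change.** In section 8.1.1:

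1. Define the primary statistic as Z = (F_B − F_A)/√(V_A + V_B), where F is the week-240 Kaplan-Meier proportion of HBsAg loss in each arm and V its Greenwood variance, compared two-sided at 5%. Delete the bracketed chi-square label.
2. Account for the randomisation factors with stratum-size (Mantel-Haenszel-type) weights: D = Σ w_h(F_Bh − F_Ah)/Σ w_h, with w_h = n_Ah·n_Bh/(n_Ah + n_Bh) and variance Σ w_h²(V_Ah + V_Bh)/(Σ w_h)². Avoid inverse-variance weights, which fail when a stratum has zero estimated variance.
3. State in advance the rule for collapsing sparse strata: which factor is dropped first, and below what number of events. With eight strata and about 5% events, some will have none.

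The cost is a few sentences in the SAP and standard software. The standard error is larger than the binomial one by about 7% under uniform timing (√1.15 = 1.07) and by about 15% at most (√1.33 = 1.15). In the three timing scenarios run, power of the unstratified Greenwood test stayed at 82% to 87%, above the planned 80%.

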8.1.2. Analysis of secondary endpoints

Analysis of secondary endpoint listed in 2.2.1a: *To compare the cumulative proportion HBsAg loss over time during and after treatment*

Cumulative proportion of HBsAg loss over time will be calculated using the product limit (Kaplan-Meier) method. HBsAg loss between two treatment groups will be compared using a two-sided two-sample stratified log-rank test. We will also describe the treatment effects in terms of hazard rates of HBsAg-loss and corresponding 95% confidence intervals. To take into account the stratification at randomization, we will use stratified Cox proportional hazard models. Comparison of hazard rates of HBsAg loss across two treatment groups adjusting for other baseline demographic, virological and clinical characteristics such as age, race, genotype, HBeAg status, initial HBV DNA level, and baseline histology will be performed using Cox proportional hazard regression. The results will be presented as incidence rate ratios of HBsAg loss and 95% confidence intervals.

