Thus, the advantages of nucleos(t)ide analogue therapy are the ease of administration, the lack of significant side effects and the consistent suppression of HBV DNA that can be achieved, particularly with the newer agents such as tenofovir DF and entecavir. While emergence of drug resistance can limit the efficacy of oral agents, a low rate of antiviral resistance (1% or less even with prolonged therapy for 4 to 5 years), is seen with entecavir and tenofovir DF, reflective of their greater potency and higher genetic barrier to resistance. As a consequence 80-90% of patients treated long-term with these agents achieve rates of marked suppression of HBV DNA levels and normal ALT levels. The advantage of peginterferon therapy is that it is administered for a limited period (6 to 12 months) and results in loss of HBsAg in a significant proportion of patients. Previous studies have shown that a one-year course of combination therapy of peginterferon and nucleos(t)ide analogue does not yield a higher response rate than a one-year course of either agent alone (21). However, these studies have been limited by the use of a nucleos(t)ide analogue with high risk of resistance (e.g. lamivudine) and a relatively short course of treatment. Thus, an obvious question is whether the combination of a limited course of peginterferon (6 or 12 months) with long-term therapy with a potent nucleos(t)ide analogue (tenofovir DF or entecavir for at least 4 years) will provide a higher rate of loss of HBsAg and ability to stop therapy without relapse. This clinical trial compares the efficacy of peginterferon plus a potent nucleotide analogue, tenofovir DF, for 24 weeks followed by monotherapy with tenofovir DF for a further 3.5 years to the efficacy of that same potent nucleotide analogue, tenofovir DF, given for a full 4 years. The primary measure of outcome will be HBsAg loss in serum 240 weeks after starting antiviral therapy.

2. Study objectives

To define the role of limited duration peginterferon alfa-2a in the presence of tenofovir for treating people with chronic hepatitis B by:

- Evaluating “off treatment” sustained responses following combination therapy consisting of peginterferon alfa-2a plus tenofovir DF versus tenofovir DF monotherapy.
- Comparing the on-treatment efficacy of initial treatment with combination therapy consisting of peginterferon alfa-2a plus tenofovir DF versus tenofovir DF monotherapy.

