2.2. Secondary endpoints

2.2.1. At week 192 :

- a. Cumulative HBsAg loss.
- b. HBeAg loss.
- c. HBsAg seroconversion.
- d. HBeAg seroconversion.
- e. ALT normalization (males \leq 30 U/L, females \leq 20 U/L).
- f. ALT \leq 38 U/L (males), \leq 25 U/L (females) corresponding to approximately 1.25 xULN.
- g. HBV DNA $<$ 1000 IU/mL.
- h. HBV DNA $<$ 20 IU/mL (Lower limit of quantification [LLOQ] of COBAS Ampliprep/COBAS TaqMan HBV v2.0 test).
- i. Absence of detectable antiviral drug-resistance HBV mutations.
- j. Sustained HBV DNA $<$ 1000 IU/mL

2.2.2. Sustained end of follow-up responses at week 240

- a. Cumulative HBsAg loss.
- b. HBeAg loss.
- c. HBsAg seroconversion.
- d. HBeAg seroconversion.
- e. ALT normalization (males \leq 30 U/L, females \leq 20 U/L).
- f. HBV DNA $<$ 1000 IU/mL.
- g. HBV DNA $<$ 20 IU/mL (LLOQ of COBAS Ampliprep/COBAS TaqMan HBV v2.0 test).

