Recruitment Retention Protocol adherence(e.g., meeting inclusion/exclusion criteria, treatment compliance) Pregnancy and outcomes in female participants	Quarterly reports for NIDDK and the appropriate oversight committees
Adverse events and Serious Adverse Events (SAE) that do not meet expedited reporting criteria	Quarterly reports for NIDDK and the appropriate oversight committees
Serious Adverse Events that meet expedited reporting criteria*	As they occur for NIDDK, DSMB, appropriate industry partner(s), and

	cumulative reports quarterly
Laboratory data	Yearly for the DSMB

The definition of adverse and serious adverse events is provided in section 7.6.1 of this protocol along with the reporting procedures in the MOP.

Stopping rules during the treatment phase (up to Week 192)

No interim analysis for efficacy is planned for this clinical trial, since the primary endpoint is expected to occur very rarely during the treatment period. As mentioned above, adverse event reporting will be quarterly throughout the study. Additional analyses will be performed at the recommendation of the DSMB if there are any concerns raised by adverse events or serious adverse events reported. The following study-wide stopping rules have been agreed upon by the clinical investigators for this interim analysis. The study will be stopped if at least one of the following occurs:

1. If the incidence of renal toxicity (defined as a persistent increase in serum creatinine >1.0 mg/dL above baseline on two successive visits 4 weeks apart or persistent grade 3 or grade 4 hypophosphatemia (requiring TDF discontinuation) exceeds 10% in either of the two study arms.
2. If the incidence of peripheral neuropathy (documented by EMG) exceeds 10%.
3. If the incidence of grade IV toxicity exceeds 10% in either of the two study arms.

Stopping rules during treatment discontinuation phase (Weeks 192 to 240)

The following has been agreed upon by the clinical investigators

1. If more than 1 participant develops clinical decompensation, no further participants will undergo treatment withdrawal until the formal review by investigators and the DSMB
2. Resumption of treatment withdrawal may occur if the DSMB and investigators determine the safety measures are adequate AND that the benefits of continued study of treatment withdrawal outweighs the risks

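### The analysis specified for the week-192 endpoint 2.2.1a has no cut at week 192, so its log-rank test and hazard ratio would include HBsAg losses from weeks 192 to 240

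*Combined protocol and SAP*

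**What the plan says.** Section 2.2 lists cumulative HBsAg loss twice as a secondary endpoint. Item 2.2.1a stands under "2.2.1. At week 192" and item 2.2.2a under "2.2.2. Sustained end of follow-up responses at week 240".

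Section 8.1.2 opens with "Analysis of secondary endpoint listed in 2.2.1a" and gives the aim as "To compare the cumulative proportion HBsAg loss over time during and after treatment". It estimates the curve by Kaplan-Meier and then states that "HBsAg loss between two treatment groups will be compared using a two-sided two-sample stratified log-rank test". Stratified and covariate-adjusted Cox models supply the effect measure. The paragraph does not mention week 192 and does not name 2.2.2a.

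Four other places bear on the point:

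- Section 2 has a separate objective, "Comparing the on-treatment efficacy of initial treatment with combination therapy", alongside the one on off-treatment response.
- Section 8.1.2.1 ties analyses to the time points of section 2.2, but for a list of events that leaves out HBsAg loss.
- Under sections 6.5 and 6.5.1, participants who meet the stopping criteria come off treatment at week 192. Those who do not meet them stay on tenofovir DF to week 240, and the text also allows for eligible participants who continue.
- Section 6.6 schedules qualitative HBsAg at weeks 216 and 240 and quantitative HBsAg at weeks 204, 216, 228 and 240, so later losses will be in the data.

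**The concern.** A log-rank test and a Cox hazard ratio summarise the whole of the follow-up they are given. Run to week 240, they do not answer whether the arms differ at week 192. If the arms separate mainly after week 192, a significant result could be filed under a week-192 endpoint that shows no difference. Section 8.1 applies a 0.05 threshold to every analysis, so such a result would count as significant.

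The treatment setting also changes at week 192, because some participants in each arm stop and others continue. One hazard ratio across both periods averages over two conditions, with weights set by where the events happen to fall.

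**Working it through.** **1. The plan's own figure.** The only relevant figure is the sample size in the section on sample size and power: 5% v 15% at week 240, two-sided 5%, 80% power. With pooled variance and no continuity correction:

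n = [1.960 × √(2 × 0.10 × 0.90) + 0.842 × √(0.05 × 0.95 + 0.15 × 0.85)]² / 0.10² = [0.8315 + 0.3521]² / 0.01 ≈ 140.1, rounded up to 141 per arm.

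Allowing for 25% loss: 141 / 0.75 = 188 per arm, 376 in total. Both figures reproduce. They belong to the week-240 primary endpoint and do not change. The documents give no power or rate for 2.2.1a.

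**2. Does any other text supply the cut-off?** The endpoint heading gives week 192, but the analysis paragraph that names the endpoint does not carry it over. Section 8.1.1 refers to a designated time point, but for the primary endpoint. The rule in 8.1.2.1 omits HBsAg loss. No cut-off is stated.

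**3. Which outputs are affected?** A Kaplan-Meier estimate at week 192 uses only events and risk sets up to week 192, so later losses leave it unchanged. The log-rank statistic and the Cox estimate sum over all event times and do change.

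**4. How much?** Keep 5% v 15% at week 240 and assume the split around week 192. Expected losses over both arms, at 141 per arm, total 141 × (0.05 + 0.15) = 28.2. Up to week 192 they are:

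- (a) 2.5% v 2.5%: 141 × 0.05 = 7.1
- (b) 2.5% v 7.5%: 141 × 0.10 = 14.1
- (c) 4% v 12%: 141 × 0.16 = 22.6

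Split (c) is close to constant hazards: 1 − 0.95^(192/240) = 4.0% and 1 − 0.85^(192/240) = 12.2%.

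Simulated rejection rates, two-sided 5%, 4,000 trials per scenario, unstratified log-rank, event times uniform within each period, no dropout:

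| Loss by week 192 | Per arm | Full follow-up | Censored at week 192 |
|---|---|---|---|
| (a) 2.5% v 2.5% | 141 | 81% | 5% |
| (b) 2.5% v 7.5% | 141 | 83% | 49% |
| (c) 4% v 12% | 141 | 81% | 71% |
| (a) 2.5% v 2.5% | 188 | 90% | 4% |
| (b) 2.5% v 7.5% | 188 | 91% | 62% |
| (c) 4% v 12% | 188 | 92% | 83% |

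The Monte Carlo standard error is at most √(0.49 × 0.51 / 4000) ≈ 0.8 percentage points. In (a), the full-follow-up rejections are correct for the 240-week curves but would be wrong as statements about week 192. In (b) and (c) the arms do differ at week 192, and the extra rejections come from events outside the endpoint's window.

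**The case against.** The best defence is that the paragraph is a joint analysis of both cumulative HBsAg-loss endpoints, 2.2.1a during treatment and 2.2.2a after it, with one cross-reference left out. That is plausible. It does not remove the problem: the label is then incomplete, and 2.2.1a still has no between-arm comparison confined to its own window.

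Several stronger readings are tempting, and the documents do not support them:

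- *Losses after withdrawal are credited to on-treatment efficacy.* Losses after week 192 are not all losses off treatment, because ineligible participants continue tenofovir DF, eligible ones may, and some restart under section 6.14.2. No text assigns 2.2.1a to the on-treatment objective either; that link is reasonable but inferred.
- *Late events would dominate the result.* Section 9.1 says that "the primary endpoint is expected to occur very rarely during the treatment period", but as the reason for having no efficacy interim. It gives no split, and 5% by week 240 is itself rare. The background reports HBsAg loss of 3% at one year and 6% at two years on tenofovir DF in HBeAg-positive disease, and higher loss after one-year courses of peginterferon (3% to 7%) than of nucleos(t)ide analogues (below 1% to 3%). Some separation before week 192 is therefore plausible.
- *Endpoint 2.2.2a has no analysis.* It lacks a paragraph under its own number, but section 8.1.1 estimates and tests cumulative HBsAg loss at week 240, and section 8.2 adds available-case analyses.

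The simulation is also simpler than the plan: it is unstratified, has no dropout and does not model the visit schedule. It illustrates direction and range and is not a forecast.

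**Conclusion.** The mismatch stands. Followed as written, section 8.1.2 would report for a week-192 endpoint a test and a hazard ratio that include losses from weeks 192 to 240, and nothing elsewhere in the documents corrects this. That these results would include the later events rests on a literal reading of 8.1.2.

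The size is uncertain. At 141 per arm the gap between the two analyses runs from 81% v 5%, if the arms are equal at week 192, to 81% v 71%, if one fifth of losses come later. All of these figures rest on an assumed split around week 192. A reader might take the 81% v 5% case as the expected effect; it is one end of the range.

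The point concerns one secondary endpoint and should be corrected before analysis. It does not threaten the trial's main conclusion.

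**What to change.** In section 8.1.2:

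1. For 2.2.1a, censor the stratified log-rank and Cox analyses at the week-192 visit. Alternatively, compare the two Kaplan-Meier estimates at week 192.
2. Assign the full-follow-up log-rank and Cox analysis to 2.2.2a and correct the cross-reference.
3. Optionally, report a separate hazard ratio for weeks 192 to 240, labelled descriptive. It conditions on participants still HBsAg-positive and in follow-up at week 192, so it is not a randomised comparison.

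This takes a wording change and one further model run. No new data are needed, since section 6.5 already schedules HBsAg at week 192. The price is fewer events and a wider interval for 2.2.1a: in the splits above, 7.1 to 22.6 expected losses instead of 28.2.
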